Treatment with a CGRP-neutralizing antibody, galcanezumab in this specific patient group, being seen in the PI's clinics on a regular basis, is rooted in the rationale of unmistakable presence of clinical signs of neurogenic inflammation in the painful territory, such as episodic swelling combined with redness/hyperemia, also relief by external cold application which typically patients with trigeminal or glossopharyngeal nerve pain abhor.

Primary Outcome Measures

Primary criterion is to establish an excellent safety profile that recapitulates the favorable data recorded in migraineurs. The primary pain-related objective is reduction of pain and reduced use of rescue and other anti-pain medication.

Inclusion Criteria

- G50.1 diagnosis (can encompass an add-on G50.0 and other headache G43.... codes), or G52.1 diagnosis code (with explicit mentioning of pain of glossopharyngeal origin) **AND** small fiber neuropathy diagnostic codes G63.3, G60.8, G62.8 (can encompass fibromyalgia diagnostic code M79.7)
- 18-80 years old
- not allergic to galcanezumab and other hu mAb biologics

Exclusion Criteria

- allergic to galcanezumab and other hu mAb biologics
- pregnancy

Study Design / Overview

We propose to treat patients open label for 12 weeks, with galcanezumab, supplied by Eli Lilly, as add-on to all other therapeutic measures. We propose to use a 240mg/120mg/120mg regime, with subcutaneous (self-)injections every 4 weeks.

To reflect pain experienced by patients, the primary read-out is pain level on a 0-10 visual analog scale. We will be prompting patients to record a daily summary read at the end of each day.

[figure not shown]
The second criterion is reduction of intake of anti-pain medication (rescue PRN or regular) which the patients will record.

Chronic pain, especially fibromyalgia pain combined with trigeminal or glossopharyngeal nerve pain, is a potent disruptor of circadian rhythm. We strongly believe that this is an important and hitherto under-appreciated contributor to individual disease burden. Therefore, the third criterion is assessment of circadian rhythm function. We will assess this by having the patient rate subjectively how energetic they feel during awake day-time. Wearable activity monitors will be used to address how many hours patients sleep per

24h period, with detailed focus on total duration of sleep/rest and duration of night-time sleep only.

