Patients will be recruited via the PI's clinics at Duke University, the Duke Clinics that typically refer to her attention and outside clinics and providers that refer to her as well, and DEDUCE database. In case of slow recruitment patient self-help and patient advocacy associations in the facial pain arena will be informed of the ongoing study to assist with recruitment. These organizations (Facial Pain Research Foundations, Facial Pain Association) are well-known to the PI.

11) Brief Statistical Analysis Plan

Only patients who complete the study will be included in the statistical analysis.

Response to treatment will be assessed by comparing pain metrics during the 90-day treatment period vs averaged 30 day "run-in". Outcome variables will consist of selected readout parameters of "pain metrics", namely pain subjective rating on VAS (0-10) and medication co-use. Additional outcome variables include circadian rhythm-associated metrics. A daily readout for each variable will be entered into their log by each patient, or by automatic activity reads from their motion tracking device. In similar manner, we will compare pain metrics during the 90-day treatment period vs 60-day post-treatment observation.

We intend to conduct the study with an n=20 patients to successfully complete the study. This selected number appears the most feasible and practicable number. We are confident that with an n=20 we will be in a position to do justice to the objective of initial assessment of the safety of galcanezumab in the condition under study, trigeminal or glossopharyngeal pain in the context of painful small fiber neuropathy/fibromyalgia.

Following completion of the study, we will have estimates of effect sizes and corresponding 95% confidence intervals providing information on the precision of the statistical estimates of treatment effect. Power analysis will be performed based on these estimates and will provide us with guidance for sample sizes of follow-up studies that aim for demonstrating effectiveness.

The statistical analysis will be based on a linear mixed model for repeated measures. The

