time course of pain metrics reported during the treatment period will be compared with metrics during the run-in baseline. The covariance matrix describing the nature of correlations between repeated measures will be selected based on Akaike information criterion and Bayesian information criterion, as guided by our statistics software, SAS/STAT15.1. p-values <0.05 will be considered statistically significant. Effects of treatments will be investigated with the introduction of treatment as a binary covariate (we will evaluate the effects of pre- and post-treatment in two different models).

Patients' anti-pain treatment response will be correlated with blood markers for pain, inflammation and miRNA, and also for genomic markers. This approach will be pursued in order to identify candidate biomarkers that pre-dispose patients to experience an effective or non-effective treatment response. In case of recording any particular safety-related parameters, correlation of these markers to safety metrics will also be conducted. Association between molecular biomarkers and pain- and activity-related metrics will be evaluated (i) at each time point separately using a linear regression model; (ii) by modeling the association across all time points and including time covariate in the linear regression model. The ensemble of these approaches will help determine the periods when pain or activity-related metrics and molecular markers co-evolve and become highly correlated.

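### The SAP promises a comparison of the time course of pain on treatment with run-in, but the only treatment term it states for the pain model is binary, so the model as written does not estimate build-up or waning, and what its one coefficient means depends on the covariance structure chosen.

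*Combined protocol and SAP*

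**What the plan says.** Section 11 sets the general method: "The statistical analysis will be based on a linear mixed model for repeated measures". It promises that the "time course of pain metrics reported during the treatment period will be compared with metrics during the run-in baseline". The treatment effect is then specified: "Effects of treatments will be investigated with the introduction of treatment as a binary covariate", with the addition that "we will evaluate the effects of pre- and post-treatment in two different models". Earlier in the section the two comparisons are described as "comparing pain metrics during the 90-day treatment period vs averaged 30 day" run-in, and "we will compare pain metrics during the 90-day treatment period vs 60-day post-treatment observation".

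The covariance structure is to be chosen by AIC and BIC. A time covariate appears once, in the regression of molecular markers on pain and activity. No day, week, interval or period-by-time term is named for the pain model.

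On dosing, Study Design / Overview says: "We propose to use a 240mg/120mg/120mg regime, with subcutaneous (self-)injections every 4 weeks". Pain is rated every day in the patient booklet (section 4). On use of the results, section 11 says: "Power analysis will be performed based on these estimates", to guide sample sizes of follow-up studies.

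**The concern.** A time course and a single 0/1 contrast are different analyses. The binary term returns one coefficient for treatment against run-in and another for treatment against follow-up. Neither model divides the treatment period.

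Two things are at stake. First, in an open-label single-arm pilot, whether pain relief builds, holds or fades across the three dosing intervals is one of the few descriptive clues to how a change arose, and the stated model does not estimate it. Second, if the effect is not constant, the coefficient is a weighted average whose weights follow from the fitted covariance. That covariance will be picked from the data, so what the headline estimate measures is not fixed in advance. The same estimate is meant to inform the planning of later trials.

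**Working it through.** **Inputs from the documents.** 30 run-in days, 90 treatment days, daily ratings, one binary term, covariance chosen by AIC/BIC, 20 completers. The plan gives no effect size, SD, onset time or correlation, so there is no figure of its own to reproduce.

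**Assumptions.** Complete daily rows; a step onset after L = 7, 14 or 28 days, followed by a constant (established) effect of 1; AR(1) with rho 0.5 or 0.8 as the example of a serial structure.

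**1. Independence or compound symmetry.** The coefficient is the treatment-period mean minus the run-in mean, so its expected value is (90 − L)/90:
- L = 7: 83/90 = 92%
- L = 14: 76/90 = 84%
- L = 28: 62/90 = 69%

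Over 84 days (the 12 weeks in the Overview) these become 77/84 = 92%, 70/84 = 83% and 56/84 = 67%.

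Under these structures, interval effects of −1.5/−1.0/−0.5 and −0.5/−1.0/−1.5 VAS points both give −1.0.

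**2. AR(1).** The generalised least squares coefficient has a closed form. Let A_n = 1 + (n − 1)(1 − rho)² and c_L = (89 − L)(1 − rho)² + (1 − rho). The expected coefficient is

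(A_30 − rho) × c_L / (A_30 × A_90 − rho²).

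- rho 0.5, L = 28: A_30 = 8.25, A_90 = 23.25, c = 15.75. Result: 7.75 × 15.75 / 191.56 = 0.64.
- rho 0.8, L = 28: A_30 = 2.16, A_90 = 4.56, c = 2.64. Result: 1.36 × 2.64 / 9.21 = 0.39.

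A random patient intercept leaves these values unchanged.

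| Assumed onset after | Independence / CS | AR(1), rho 0.5 | AR(1), rho 0.8 |
|---|---|---|---|
| 7 days | 92% | 85% | 51% |
| 14 days | 84% | 78% | 47% |
| 28 days | 69% | 64% | 39% |

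The cause is the weighting: a serial structure gives most weight to the days next to the switch. By the same least-squares calculation at rho 0.8, the fading profile above gives −1.21 and the building profile −0.79. The distortion can therefore go either way.

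**3. Follow-up sample size.** At an unchanged SD, planning from the 90-day mean when the target is the established effect multiplies the sample size by (90/(90 − L))²: (90/83)² = 1.18, (90/76)² = 1.40, (90/62)² = 2.11. This applies only if the follow-up endpoint is late-period pain.

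**4. Precision cost of an interval contrast.** Assume 20 patients, daily SD 1.5, rho 0.3 to 0.8, and a between-patient SD of the treatment effect of 1 to 2. The variance of a contrast is (effect variance + variance of the difference in phase means)/20. For the last 30 days against run-in, compared with the 90-day mean, the SE ratio runs from 0.462/0.457 = 1.01 (rho 0.3, effect SD 2) to 0.328/0.296 = 1.11 (rho 0.8, effect SD 1).

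**The case against.** **The SAP is brief and does not list every fixed effect.** A time term beside the binary one is compatible with the wording. This stands in part. A reader might infer that build-up or waning cannot be seen in this trial. The documents do not support that: ratings are daily, and plots or an added term would show the shape. What is true is that the stated pain model does not estimate it, while a time term is stated for the biomarkers.

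**A whole-period average is a legitimate target.** This stands. The fix keeps it as the main summary.

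**The binary term does not, in general, weight all days alike.** A reader might infer that day 1 counts the same as the last week, and that fading and building relief always give the same coefficient. That holds only under independence or compound symmetry, and the SAP leaves the structure open. The correction does not help the plan: for the assumed delayed onsets the dilution is larger under AR(1).

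**The size rests on an onset the documents do not give.** This stands. With onset at 7 or 14 days and equal weighting, the loss is only 8% to 16%.

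**Follow-up studies need not be oversized.** This stands. The documents name no follow-up endpoint. If it is the whole-period mean, that mean is the right planning input and nothing is inflated.

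**The last interval is not an undiluted drug effect.** This stands. In one open-label arm it also contains regression to the mean, secular trend and expectation effects, so planning from it could leave a later trial underpowered.

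**The primary criterion is safety and n = 20 rests on feasibility.** This limits the weight of the point but does not remove it, because the pain estimates are to be used for planning.

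**Conclusion.** The concern holds in a limited form. Section 11 promises a time-course comparison and states a treatment term that does not deliver one. For an effect that changes within the treatment period, the coefficient is the 90-day mean only under independence or compound symmetry. Under a serial structure it leans towards the days around the switch. For an assumed 28-day onset the same underlying effect would be reported as 69%, 64% or 39% of its established size, depending on the covariance. If onset is immediate and the effect constant, every structure gives the full effect and nothing is lost.

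These sizes depend on assumed onset times and correlations. The documents do not show that the effect is delayed, that AR(1) will be selected, or that any later trial will be the wrong size. The change should be made because it is cheap and fixes the meaning of the estimate in advance; the trial's safety objective is unaffected.

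**What to change.** In the same mixed model, enter daily run-in rows rather than one averaged value, and replace the binary term with a four-level phase factor: run-in, then the intervals after the first, second and third injection. Three 30-day blocks are the alternative if the 90-day window is kept. Say which is used and where the third interval ends, since three 4-week intervals cover 84 days.

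Report:
- the three contrasts against run-in, each with a 95% CI;
- a 2-df test that the three intervals are equal;
- the equally weighted average of the three contrasts, as the main summary.

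For planning, use the contrast that matches the follow-up endpoint: the average if that endpoint is the whole-period mean, the last interval only if it is late-period pain. State that in a single open-label arm all of these contrasts also contain regression to the mean, secular trend and expectation effects.

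The phase factor recovers changes that fall at interval boundaries whatever the covariance. Some dependence on the covariance remains for changes inside an interval, so show plain phase means beside the model estimates.

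The cost is SAP wording, two extra fixed-effect parameters and slightly wider interval CIs (SE about 1% to 11% larger for the last interval under the assumed variances). No new data or visits are needed.

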That human migraine can be treated effectively with episodic injections of anti-CGRP antibodies begets the question whether these newly prescribe-able medications can be repurposed for other trigeminal pain conditions and the related glossopharyngeal cranial nerve pain which are known to involve neurogenic inflammation. Another pain condition with poor treatment options for sufferers is fibromyalgia, especially fibromyalgia with associated small fiber neuropathy which leads to systemic de-afferentiation of patients' sensory system. In this condition, there is strong evidence for presence of neurogenic inflammation, and it is a rational concept that neurogenic inflammation contributes to disease pathogenesis and especially to the dominating clinical symptom of pain.

We propose to treat patients (targeting enrollment of n=20) who suffer from trigeminal or glossopharyngeal nerve pain in the context of painful small fiber neuropathy. We predict that recruitment of these patients will not be a challenge in the PI's clinics, based on previous experience and ongoing referral practice. Primary criterion is to establish an excellent safety profile that recapitulates the favorable data recorded in migraineurs. The primary pain-related objective is reduction of pain and reduced use of rescue and other anti-pain medications.

Secondary pain-related objectives are improvement of circadian rhythm impairment by galcanezumab, improvement of serum markers for chronic inflammation including protein/peptide as well as small non-coding RNA molecules, and discovery of DNA polymorphisms that predispose treated patients to accentuated responses of either lack of response or particularly potent response.

Clinical Collaborators

[name] MD, Duke Neurology
[name] MD

Hypothesis/ Purpose

We hypothesize that the proposed galcanezumab regimen will be found safe in our patient population, and that provisional evidence of its effectiveness will become apparent. We envision galcanezumab to target neurogenic inflammation in the trigeminal territory and neurogenic inflammation associated with small fiber neuropathy/fibromyalgia.

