In addition, we propose to detect systemic circulatory microRNAs. These molecules will be identified by RNA-seq starting with small RNA-preparation from patients' serum. This approach is preferred over a candidate approach since it is maximally unbiased. We believe that an unbiased approach will be more suitable because pain-associated circulatory miRNA markers are not firmly established, therefore a "candidate approach" is not even feasible. With an open, unbiased discovery approach of miRNAseq we minimize the risk to miss anything of relevance. The number of miRNAs is considered currently slightly >2000, thus very roughly 1/10 of the number of all protein-coding genes. MicroRNAs have been established robustly as biomarkers in specific malignancies, also with chronic inflammation, so that a tentative association with specific pain conditions appears an appealing opportunity to make these discoveries in our patient population.

Baseline blood draw (and only at that time point because it will not change through treatment) will also include preparation of genomic DNA from white blood cells to sequence the patients' genomic DNA whole-exome. Having these data available will position us favorably so that we can identify any genetic abnormalities (e.g. in pain-associated voltage-gated sodium channels, pain-TRP channels, inflammation-associated genes) in our patients. First we will be analyzing the genomic DNA profile for presence of pain susceptibility genes in known genes and their respective families, such as voltage-gated sodium channels, neurogenic inflammation pathway, opioid receptor signaling, MRGPR-X related pathway, pain-TRPs and associated proteins, β -adrenergic signaling, COMT pathways, algogenic lipid mediator pathways, and more. After identification of particular high-responders and low/non-responders, we will try to identify association of these particular response patterns with any measured biomarker, including DNA polymorphisms, miRNA, lipid, protein/peptide markers.

3) Data Safety Monitoring Board (DSMB)

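### Regressing response on whole-exome variants in 20 completers, with no minimum carrier count and no multiplicity rule, turns single-carrier variants into outlier tests of individual patients

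*Combined protocol and SAP*

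**What the plan says.** The Abstract lists among the secondary objectives the "discovery of DNA polymorphisms that predispose treated patients to accentuated responses of either lack of response or particularly potent response". Section 2 (Blood draw: detailed analysis) plans to take "genomic DNA from white blood cells to sequence the patients' genomic DNA whole-exome" at baseline, and adds: "Having these data available will position us favorably so that we can identify any genetic abnormalities". It starts with an open-ended list of pain-related gene families. It then sorts out high-responders and low or non-responders, and looks for association of those patterns with any biomarker measured, DNA polymorphisms included.

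Section 11 (Brief Statistical Analysis Plan) gives the analysis: "Patients' anti-pain treatment response will be correlated with blood markers for pain, inflammation and miRNA, and also for genomic markers". The aim is candidate markers of good or poor response. For molecular biomarkers it names linear regression, by time point and across time. The only significance rule in the plan is "p-values <0.05 will be considered statistically significant", which stands in the paragraph on the mixed model.

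On numbers, section 11 says "We intend to conduct the study with an n=20 patients to successfully complete the study" and "Only patients who complete the study will be included in the statistical analysis". The reason given for 20 is feasibility: "This selected number appears the most feasible and practicable number".

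The plan contains no minimum number of carriers, allele-frequency filter, gene-level collapsing, multiplicity correction or replication step. It does not name a correlation coefficient.

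**The concern.** Exome data from 20 people can be expected to contain variants seen in only one of them. Regressing response on such a variant compares one patient with the other 19. The result shows whether that patient's response is unusual and carries no separate information about the variant. Every variant private to that patient has the same 0/1 pattern across the 20 patients, so all of them receive the same p-value and are declared, or not, as a block.

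A secondary objective is to find variants that predispose to strong or absent response, and the protocol expects the study to guide larger trials and possibly a personalised approach. If the analysis is run as written, part of the reported list may simply be the private variants of whoever had an extreme pain change.

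**Working it through.** **Inputs from the documents.** n = 20 completers; p<0.05; linear regression; no carrier minimum. The plan gives no power or error-rate figure for this analysis, so there is nothing of its own to reproduce.

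**Assumptions that the documents do not give.** Two-sided testing, with both directions of response counted; the 0.05 threshold applies to genomic tests; each patient has at least one private variant among those tested; a stated shape for the response distribution.

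**Step 1: what the test is.** Let the marker be 1 for patient i and 0 for the rest. With d = response of patient i minus the mean of all 20, SS = total sum of squares about the mean, and r = d² × 20/19:

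t² = r / [(SS − r)/18], on 18 df.

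This is the usual single-outlier statistic. A numerical check on simulated data gave the same p-value from Pearson correlation, linear regression and the pooled t-test of 1 against 19.

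**Step 2: how extreme a patient must be.** The critical value is t = 2.101, so t² = 4.414. Then r/SS = 4.414/(18 + 4.414) = 0.197. With SS = 19s², d² = 0.197 × 19s² × 0.95 = 3.55s², so |d| = 1.89s. A patient about 1.9 sample SDs from the mean of the 20 is enough.

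**Step 3: how often this happens with no genetic effect.** In 400,000 simulated trials with normal responses:

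- error rate per single-carrier pattern: 5.0%
- at least one patient flagged: 77.7%
- exactly one patient: 56%; two or more: 21%
- mean number flagged: 20 × 0.05 = 1.0

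Treating the 20 tests as independent would give 1 − 0.95²⁰ = 64.2%. The simulated figure is higher because the tests share one mean and one variance.

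**Step 4: sensitivity.** Probability that at least one patient is flagged:

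| Setting | Probability |
|---|---|
| Uniform responses | 22% |
| Two-group mixture | 65% |
| Normal | 78% |
| t, 4 df | 91% |
| Normal, 15 completers | 66% |
| Normal, 18 completers | 74% |
| Normal, p<0.01 | 20% |
| Normal, p<0.05/20 = 0.0025 | 5.0% |

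**Step 5: other tests.** An exact rank test of 1 against 19 has a smallest two-sided p of 2/20 = 0.10. Fisher's exact test of carrier status against responder status has a smallest p of 1/20 = 0.05, reached only with a single responder or a single non-responder, and that is not below 0.05. Under either test the flag rate is 0%.

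**Step 6: is a multiplicity correction alone enough?** Suppose only private variants are tested and each patient has the same number. Benjamini-Hochberg at 5% then behaves like 20 tests, because the p-values within a patient are copies. It gives a false finding in 5% of null trials with normal responses but 28% with t (4 df) responses.

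**Step 7: is a carrier minimum alone enough?** A minimum removes the single-carrier tests. For variants with 5 to 10 carriers tested at p<0.05 with no genetic effect, at least one is still falsely declared in 42% of trials for 10 variants, 93% for 50 and 99.8% for 100 (about 5 false hits). Both rules are needed.

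**The case against.** The strongest reply is that the plan does not clearly assign regression to DNA. Section 11 says only that response is correlated with genomic markers. Its regression sentence deals with associations over time points, which suits serum markers better than a baseline-only exome. The one concrete genetic step, in section 2, compares responder groups. If that means Fisher's test, or if the correlation is rank-based with an exact p-value, no single-carrier variant can reach p<0.05. This stands, and it makes the 78% conditional. It does not remove the gap: regression is the only method named for molecular biomarkers, and a test that can never declare a single-carrier variant is itself a reason not to test such variants one by one.

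It can also be said that this is mainly missing multiplicity control, since the per-test error is 5.0% and the rate falls to 20% at p<0.01. That is largely right for the size of the figure. A reader might infer a fault independent of the threshold; the numbers do not support that. What does not depend on the threshold is the meaning of the test and the block of identical p-values. Step 6 shows that correction alone is unreliable when responses have heavy tails.

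Finally, the output is described as candidate biomarkers from a pilot, and no safety, pain or treatment decision rests on it. That stands and limits the weight of the point.

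**Conclusion.** The point holds in conditional form. With regression or Pearson correlation, two-sided p<0.05 applied to the genomic tests, roughly normal responses and at least one private variant tested per patient, about 78% of trials with no genetic effect would flag at least one patient's private variants. The range over the response shapes above is about 22% to 91%; exact rank or Fisher tests give 0%.

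Two stronger readings are not supported. A reader might infer that one extreme patient supplies the whole list of markers. Two or more patients are flagged in 21% of null trials, and variants shared by several patients add false positives of their own. A reader might also want to state how many false markers one trial would yield. That depends on the number of private variants per patient, which the documents do not give, and the search begins with selected gene families.

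The consequence is confined to an exploratory secondary objective. The safety and pain analyses are unaffected.

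**What to change.** Add to section 11:

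1. Single variants are tested only if at least a stated number of analysed patients carry them and at least that number do not. Five and five is an example; the documents do not determine the cut-off.
2. Rarer variants are collapsed into one burden score for each gene family named in section 2, with the open-ended list closed before analysis. Each score is tested against one named response measure (for example, change in mean VAS from run-in to treatment), with Holm correction across families.
3. The single-variant tests also receive a multiplicity correction, by false discovery rate or permutation.
4. Variants below the minimum are listed by patient without a p-value.
5. All genomic results are labelled hypothesis-generating.

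The cost is SAP wording and changed analysis code. No further patients, samples or visits are needed. The downside is that a causal variant seen in one patient is listed but not tested; little is lost, because one carrier among 20 cannot separate the variant's effect from everything else particular to that patient.
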